### **2.4.2 Prior, concomitant, and post therapies**

Prior and post medication/therapies are not applicable in this roll-over study. The information of concomitant medication is not collected.

## **2.5 Analysis of the primary objective**

### **2.5.1 Primary endpoint**

The primary objective is to evaluate long term safety as assessed by the occurrence of AEs/SAEs.

Variables see Section 2.8

### **2.5.2 Statistical hypothesis, model, and method of analysis**

No hypothesis will be tested.

### **2.5.3 Handling of missing values/censoring/discontinuations**

Not applicable.

### **2.5.4 Supportive analyses**

No supportive analysis is planned.

## **2.6 Analysis of the key secondary objective**

No key secondary efficacy objectives are analyzed.

## **2.7 Analysis of secondary efficacy objective(s)**

### **2.7.1 Secondary endpoints**

The secondary objective of the study is to evaluate clinical benefit as assessed by the investigator. The secondary endpoint is the proportion of patients with clinical benefit as assessed by the investigator at scheduled visits.

### **2.7.2 Statistical hypothesis, model, and method of analysis**

No statistical analyses will be performed on secondary endpoint. Data will be used only for descriptive summary of patients remaining on drug – as needed during the conduct of the study. SAEs reported to the safety database will be reviewed and reported as part of the regular pharmacovigilance activities.

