**Table 3-1 Objectives and related endpoints**

Objective	Endpoint	Analysis
Primary		
To evaluate long term safety data	Frequency and severity of AEs/SAEs	Refer to Section 10.4
Secondary		
To evaluate clinical benefit as assessed by the investigator	Proportion of patients with clinical benefit as assessed by the investigator at scheduled visits	Refer to Section 10.5

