#### **10.5.2 Other secondary efficacy objectives**

[figure not shown]
The secondary objective of the study is to evaluate clinical benefit as assessed by the investigator. Proportion of patients with clinical benefit as assessed by the investigator will be summarized at scheduled visits.

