## **2 Statistical methods**

### **2.1 Data analysis general information**

Data will be analyzed by Novartis using SAS Version 9.3. Only data reported in the database of this protocol will be included in the analyses. Patient data from the parent study will not be taken into account.

Summary tables will be provided for patient disposition, demographic data and treatment exposure. All data collected on the database will be listed, using all patients enrolled in this study.

Categorical data will be presented as frequencies and percentages. For continuous data, mean, standard deviation, median, minimum, and maximum will be presented, unless otherwise stated.

The original protocol was released on 07-Dec-2012. Protocol amendment 1 (PA1) was released on 18-Mar-2016. In this amendment the primary endpoint was changed to safety to better characterize the long-term safety of the compound. In addition, the protocol has been amended to include the collection of all AEs (including non-serious AEs) and an investigator attestation of continued clinical benefit. Additional eCRFs were added to collect data related to

- Investigator attestation of clinical benefit at every quarterly visit
- All adverse events (based on original protocol only SAEs were collected and all SAEs were only collected in ARGUS safety database)
- Relevant medical history/current medical conditions
- Monthly at home pregnancy testing for female patients of child bearing potential (serum/urine)
- Study evaluation completion at the end of the 30 day safety follow up
- Related imaging, drug use 6 months prior to liver event, pathology, medical history possibly contributing to liver dysfunction, local laboratory results (viral serology, autoimmune, immunoglobulin, liver function tests), overview, potential impact of alcohol use, acetaminophen/paracetamol pertaining to liver event (only when drug-induced liver injury (DILI) cases occur)

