## **2.2 Analysis sets**

The safety set will be used for statistical analysis and data reporting.

The Safety Set includes all patients who received at least one dose of study drug after enrolling into the roll-over protocol.

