### **2.7.3 Handling of missing values/censoring/discontinuations**

Not applicable.

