## **4 Change to protocol specified analyses**

No change from protocol specified analysis is planned.

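### SAP 2.7.2 drops the protocol's by-visit summary of clinical benefit, while SAP 4 declares no change (minor)

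*SAP*

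**What the plan says.** Protocol Table 3-1 gives one secondary endpoint: "Proportion of patients with clinical benefit as assessed by the investigator at scheduled visits". Protocol 10.5.2 states the analysis, and the data-analysis row of the protocol summary says the same: "Proportion of patients with clinical benefit as assessed by the investigator will be summarized at scheduled visits".

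The SAP takes over the endpoint in Table 1-1, which refers to SAP 2.7 for the analysis, and in 2.7.1: "The secondary endpoint is the proportion of patients with clinical benefit as assessed by the investigator at scheduled visits". SAP 2.7.2 then reads: "No statistical analyses will be performed on secondary endpoint. Data will be used only for descriptive summary of patients remaining on drug", with a rider that makes even this summary depend on need during the study. Under the heading "Handling of missing values/censoring/discontinuations", SAP 2.7.3 enters only that it does not apply. SAP 4 states: "No change from protocol specified analysis is planned".

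Two general provisions also bear on the point. SAP 2.2 says "The safety set will be used for statistical analysis and data reporting", and SAP 2.1 says "All data collected on the database will be listed, using all patients enrolled in this study".

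**The concern.** The protocol promises a table and the section of the SAP that should specify it withdraws it, yet the SAP's own statement of changes says nothing has changed. A programmer who follows SAP 2.7.2 would produce no by-visit proportion. The study report would then lack the summary of its only secondary endpoint, with no declared reason.

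Putting the protocol's sentence back is not quite enough. Patients judged no longer to benefit stop treatment (protocol 6.1.5), and protocol Table 7-1 schedules no benefit confirmation at the End of Treatment visit. Those who lose benefit therefore tend to drop out of the numerator and the denominator together. The attestation form also did not exist for the early part of the study. Without a stated N, a reader could not tell what a reported percentage refers to.

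**Working it through.** The documents give no result, target or sample-size figure for this endpoint, so there is no stated figure to reproduce. The check compares texts and then does simple arithmetic on the patient counts.

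**1. Planned analysis against SAP instruction.**
- Protocol 10.5.2 and summary: a descriptive proportion with benefit at each scheduled visit, without condition.
- SAP Table 1-1 and 2.7.1: the same endpoint.
- SAP 2.7.2: no statistical analysis; the data serve only a conditional summary of who is still on drug.
- SAP 4: no change.

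The third item cannot be reconciled with the first, and it makes the fourth incorrect.

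**2. Does reading SAP 2.7.2 as ruling out inference only resolve it?** No. The protocol's analysis was already descriptive, so excluding inference would have left it in place. The second sentence is what removes it, because it restricts how the data may be used.

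**3. Does another SAP table supply the summary?**
- SAP 2.1 names summary tables for disposition, demographics and exposure, and lists all collected data. Attestations are therefore listed, not summarised.
- SAP 2.3.1 tabulates treatment status and the main reason treatment ended. Progression is among the withdrawal reasons in protocol 7.1.5.1, so this is related information, but it is by patient and not by visit.
- SAP 2.14 allows occasional summaries of patients on drug. These are optional and do not use the attestation.
- SAP 2.8 covers exposure and safety only.

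**4. How many patients could have an attestation?** Inputs from SAP 2.1: 34 patients in all; when Amendment 1 was released, 32 were enrolled, of whom 21 were ongoing and 11 had discontinued; 2 consented afterwards; the attestation form was added with that amendment.
- Consistency: 21 + 11 = 32 and 32 + 2 = 34.
- Ceiling on patients ever attested: 21 + 2 = 23, and 23/34 = 67.6%.
- Never attestable: 34 − 23 = 11, and 11/34 = 32.4%.

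**5. Why N must be stated.** The documents give no benefit counts, so the following are assumed values for illustration. Suppose every patient attested at some visit is confirmed as benefiting:

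| Attested and confirmed (assumed) | Among attested | Of 23 | Of 34 |
|---|---|---|---|
| 10 | 100% | 43.5% | 29.4% |
| 15 | 100% | 65.2% | 44.1% |
| 20 | 100% | 87.0% | 58.8% |

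The same data give 100% or 29.4% to 58.8%, depending only on whether N is the attested patients or all 34.

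**The case against.** The strongest defence is that little is lost. The quarterly attestation asks the investigator both to confirm benefit and to confirm that treatment may go on, so being confirmed and being on drug nearly coincide at a visit. A summary of patients remaining on drug could be read as the benefit summary among those still treated. SAP 2.3.1 already shows how many stopped and why, every attestation is listed, and SAP 2.7.1 together with the general rule of frequencies and percentages still points to a summary. The sentence may simply be left over from SAP version 1.0, when the primary endpoint was the number of patients receiving everolimus. That is an inference, but a reasonable one.

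Much of this stands, and it is why the point is minor. It does not remove the conflict. A patient can be on drug with no attestation, as all were before Amendment 1. The on-drug summary is conditional where the protocol's is not. A disposition table has no visit dimension.

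It is also fair to say that the ordinary denominator for a descriptive by-visit proportion is the patients assessed at that visit, and that no elaborate rule is called for. A reader might infer that stopped patients must be carried forward to the dates on which later visits would have fallen due, or that visits must be renumbered from the first attestation. The documents do not support requiring this. Protocol 7.1.5 and 7.1.6 provide for no study visits beyond the 30-day safety follow-up, and Table 7-1 numbers visits from enrolment. Such a rule would be a new estimand, not the protocol's analysis.

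**Conclusion.** The conflict holds: SAP 2.7.2 contradicts protocol 10.5.2, the protocol summary, and the SAP's own Table 1-1 and 2.7.1, and SAP 4 is incorrect as it stands. Taken literally, the only secondary endpoint is listed but not summarised by visit. Severity is minor, because the endpoint is descriptive, no decision depends on it, and the primary safety analysis is unaffected.

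The one figure that follows from the documents is the ceiling of 23 of 34 patients (67.6%) who could ever be attested. It assumes that all 34 were dosed (the size of the Safety Set is not given), that there was no retrospective attestation, and, to be reached, that all 21 ongoing patients had a later attestation visit. It is an ever-attested ceiling, not a by-visit proportion.

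Three stronger readings are not supported.
- The endpoint has not been abandoned or its data lost: the SAP still defines it and lists the attestations.
- The proportion among attested patients is pushed towards 100% but not fixed there, since a negative attestation at a visit remains possible.
- The number of quarterly visits missed before Amendment 1 cannot be worked out: that amendment introduced the quarterly schedule, and the earlier one is not given. Nor would the enrolment visit be informative, because current benefit is an entry criterion (protocol 5.2).

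**What to change.** Replace the first two sentences of SAP 2.7.2 with the protocol's analysis: n/N and percent with clinical benefit at each scheduled visit, with N stated in the table. Patients attested at that visit is the natural choice. Beside it, show how many Safety Set patients have no attestation at that visit, in three exclusive lines:
- stopped for disease progression;
- stopped for other reasons;
- not assessed, including the 11 who left before the form existed.

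Replace the entry in SAP 2.7.3 with a reference to this display.

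If the sponsor prefers not to produce the by-visit summary, say so in SAP 4 as a departure from protocol 10.5.2, and bring SAP Table 1-1 and 2.7.1 into line.

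The cost is a few lines of SAP text and one table. It uses the attestations and the date and reason for stopping treatment that are already collected, so no new data are needed. The display may look less favourable than the proportion among attested patients alone.

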### **2.7.3 Handling of missing values/censoring/discontinuations**

Not applicable.

## **2.8 Safety analyses**

The assessment of safety will be based mainly on the frequency of AEs and SAEs.

### **Analysis set and grouping for the analyses:**

The overall observation period will be divided into two mutually exclusive segments:

1. on-treatment period: from day of first dose of study medication in the roll-over study to 30 days after last dose of study medication

2. post-treatment period: starting at day 30+1 after last dose of study medication.

### 2.8.1 Exposure to study treatment

Exposure will be assessed for both Everolimus and Everolimus + Sandostatin LAR.

The following analyses will be performed to assess study treatment exposure:

- Duration of study drug exposure in years;
- Cumulative dose;
- Actual dose intensity;
- Dose adjustments and discontinuation;

Separate table and plot for on-treatment period and AEs/SAEs collection period in clinical database on patient level will be generated to reflect the proportion of safety data collection within the overall treatment period.

### 2.8.2 Adverse events (AEs)

Verbatim terms will be coded to lower-level terms in the Medical Dictionary for Regulatory Activities (MedDRA). AEs will be coded to MedDRA. An assessment of severity grade will be made using NCI-CTCAE v4.03. Summary tables for adverse events (AEs) will include only AEs that started or worsened during the on-treatment period, the *treatment-emergent* AEs. The incidence of treatment-emergent adverse events (new or worsening from baseline) will be summarized by System Organ Class (SOC) and or Preferred Term (PT), severity (CTC Grade 1-4, 5 Death is excluded), type of adverse event, relation to study treatment.

Since safety data collection was changed in the protocol amendment released on 18-Mar-2016, CTC grade were captured in the RDC clinical database only after the protocol amendment. All SAEs including AESIs reported as SAEs were captured in ARGUS safety database throughout the study.

Thorough manual review was implemented to ensure SAEs reported both in ARGUS and RDC databases were uniquely matched without any missing or overlapped inputs.

Hence, AEs/SAEs from both ARGUS safety database and RDC clinical database will be summarized separately to ensure comprehensive and transparent safety data reporting. Global protocol amendment date (18-Mar-2016) as a general cutoff date will be applied to analyze safety data from RDC clinical database.

The following AE summary tables will be provided:

I. from Safety Database (ARGUS):

- All SAEs throughout the study
  - SAEs regardless of study treatment relationship by primary system organ class and preferred term
  - SAEs suspected to be study treatment relationship by primary system organ class and preferred term

- All AESI reported as SAEs as per protocol throughout the study
  - Serious AESIs regardless of study treatment relationship by safety topic and preferred term

II. from Clinical Database (RDC):

- AEs (non-serious AE and AESI) after protocol amendment
  - AEs regardless of study treatment relationship
    - a. by primary system organ class, preferred term and maximum CTC grade
    - b. by primary system organ class and preferred term
  - AEs suspected to be study treatment related
    - a. by primary system organ class, preferred term and maximum CTC grade
    - b. by primary system organ class and preferred term
  - AEs leading to study drug discontinuation regardless of study drug relationship by primary system organ class and preferred term
  - AEs resulting in dose adjustment or interruption regardless of study drug relationship by primary system organ class and preferred term
  - AEs requiring additional therapy and concomitant medication regardless of study drug relationship by primary system organ class and preferred term
  - AESIs regardless of study treatment relationship
    - c. by primary system organ class, preferred term and maximum CTC grade
    - d. by primary system organ class and preferred term
  - AESIs suspected to be study treatment related
    - c. by primary system organ class, preferred term and maximum CTC grade
    - d. by primary system organ class and preferred term
  - AESIs leading to study drug discontinuation regardless of study drug relationship by primary system organ class and preferred term
  - AESIs resulting in dose adjustment or interruption regardless of study drug relationship by primary system organ class and preferred term
  - AESIs requiring additional therapy and concomitant medication regardless of study drug relationship by primary system organ class and preferred term
- SAEs after protocol amendment
  - SAEs regardless of study treatment relationship by primary system organ class and preferred term
  - SAEs suspected to be study treatment relationship by primary system organ class and preferred term

For legal requirements of ClinicalTrials.gov and EudraCT, two required tables on treatment-emergent non-serious AEs with an incidence greater than 5% in clinical database, and on-treatment deaths and treatment-emergent SAEs in ARGUS safety database will be provided by

system organ class and preferred term using the safety set. The rule for the calculation of the number of occurrences is detailed in the Appendix section 5.2.

All of these tables will display the number and percent of patients that experience the given event and will display events by MedDRA. Events will be displayed alphabetically for SOC and PT. All safety data (including those from the post-treatment periods) will be listed and those collected during the post-treatment period are to be flagged. The following listings will also be generated:

- Listing of AEs leading to study drug discontinuation
- Listing of AEs leading to dose adjustment or interruption
- Listing of SAEs in ARGUS safety database
- Listing of SAEs in RDC clinical database

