Table 7-1: Updated to include investigator attestation of clinical benefit at every quarterly visit, collection of all adverse events, relevant medical history, monthly at home pregnancy testing for female patients of child bearing potential and the study evaluation completion eCRF page at the end of the 30 day safety follow up.

Section 7.1.2.3: Updated to reflect collection of demographics and relevant medical history.

Section 7.1.4: Updated to specify amount of drug supply to be provided, visits are quarterly, and that the investigator is required to confirm that the patient continues to have clinical benefit at every visit and may continue receiving study treatment.

Section 7.1.5: Section name updated.

Section 7.1.5.1: Section name updated in addition to adding new language.

Section 7.1.6: Section name updated. Added stipulation that adverse events be collected.

Section 7.1.6.1: Added new section for study evaluation completion.

Section 7.1.7: Added Lost to follow up language.

Section 7.2.1: Updated to specify that the investigator is required to confirm that the patient continues to have clinical benefit at every visit and may continue receiving study treatment.

Section 7.2.2: Updated pregnancy testing language.

Section 8: Updated with new AE/SAE reporting process.

Section 10: Updated statistical analysis section based on revised study objectives.

Section 11.4: Added reference to Section 4.4.

Section 13: Removed references no longer used.

References to the parent protocol have been removed in favor of a newer source that can be used (for example, the IB), as applicable. The protocol summary has also been updated to reflect the above changes, as applicable.

A copy of this amended protocol will be sent to the Institutional Review Board (IRBs)/Independent Ethics Committee (IECs) and Health Authorities.

The changes described in this amended protocol require IRB/IEC approval prior to implementation.

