### **12.1 Amendments to the protocol**

Any change or addition to the protocol can only be made in a written protocol amendment that must be approved by Novartis, Health Authorities where required, and the IRB/IEC/REB. Only amendments that are required for patient safety may be implemented prior to IRB/IEC/REB approval. Notwithstanding the need for approval of formal protocol amendments, the investigator is expected to take any immediate action required for the safety of any patient included in this study, even if this action represents a deviation from the protocol. In such cases, Novartis should be notified of this action and the IRB/IEC at the study site should be informed according to local regulations (e.g. UK requires the notification of urgent safety measures within 3 days) but not later than 10 working days.

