However, at the time of global protocol amendment was released, 32 out of 34 patients were enrolled; 21 patients ongoing; 11 patients had already discontinued the study. Only 2 patients consented after PA1 approval. Therefore, 32/34 patients did not have AEs collected in eCRFs before PA1, ~30% of enrolled patients had AEs reported in RDC clinical database after PA1, and ~50% of SAEs occurred before PA1 were not reported in RDC. Due to this, safety data from both ARGUS safety database and RDC clinical database will be analyzed separately for comprehensive and transparent safety data reporting in final CSR. See section 2.8.2 in detail.

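### RDC adverse-event percentages use one global release date and an all-treated denominator, so patients never observed for non-serious AEs count as event-free

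*SAP*

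**What the plan says.** SAP 2.8.2 sets one lower limit for every RDC safety table: "Global protocol amendment date (18-Mar-2016) as a general cutoff date will be applied to analyze safety data from RDC clinical database". SAP 2.1 says what that date is: "Protocol amendment 1 (PA1) was released on 18-Mar-2016".

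The protocol separates release from implementation. Its Amendment 01 section says: "The changes described in this amended protocol require IRB/IEC approval prior to implementation". Section 12.1 gives the one exception: "Only amendments that are required for patient safety may be implemented prior to IRB/IEC/REB approval". Before the amendment, according to SAP 2.1, "based on original protocol only SAEs were collected and all SAEs were only collected in ARGUS safety database".

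SAP 2.2 defines a single analysis set, the Safety Set, containing every patient with at least one roll-over dose. SAP 2.8.2 reports number and percent of patients, and names the safety set for the two registry tables. SAP 2.5.3 has no rule for missing data. SAP 2.8 ends the on-treatment period 30 days after the last dose.

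On patient numbers at release, SAP 2.1 gives "32 out of 34 patients were enrolled; 21 patients ongoing; 11 patients had already discontinued the study". It adds that two patients consented after approval of the amendment, and that roughly "30% of enrolled patients had AEs reported in RDC clinical database after PA1". SAP 2.8.1 plans a table and plot in which the on-treatment period and "AEs/SAEs collection period in clinical database on patient level will be generated".

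**The concern.** The primary endpoint is frequency and severity of AEs/SAEs. For non-serious events and for CTC grades, RDC is the only source. A percentage is interpretable only if the patients in the denominator could have had the event recorded. Here the denominator includes patients whose on-treatment period was over before anyone was asked to record non-serious events for them. They enter as patients without the event, not as patients without data.

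There are two such groups. The larger is documented: the 11 patients who had discontinued by 18-Mar-2016. The smaller follows from using release in place of local implementation: any of the 21 ongoing patients who stopped before the amendment took effect at their site. Both push the non-serious AE percentages down, on an endpoint introduced to characterise long-term safety better.

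**Working it through.** **1. Reproduce the SAP's counts.** 32 + 2 = 34 enrolled in total; 32 - 11 = 21 ongoing at release. The approximate 30% is nearest to 10 patients: 10/34 = 29.4% (9/34 = 26.5%, 11/34 = 32.4%). The SAP gives no count, so 10 is an assumption.

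**2. Patients who could be observed.** 21 + 2 = 23 of 34 (68%), plus any of the 11 whose 30-day tail reached the start of collection, minus *g*, the number of the 21 whose on-treatment period ended before local implementation. The SAP does not use 23 anywhere; its default denominator is 34.

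**3. Illustrative size of *g*.** The documents give no approval dates, no lag and no count of patients leaving in the interval. Assumed lags *L*: 3, 6 and 12 months. The discontinuation rate comes from 11 of 32 patients stopping between study opening on 13-May-2013 (protocol, amendment rationale) and 18-Mar-2016, which is 1040 days, or T = 2.85 years:

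- all 32 enrolled at opening: h = -ln(21/32)/2.85 = 0.148 per year;
- uniform accrual: 1 - (1 - exp(-hT))/(hT) = 11/32 gives h = 0.320 per year.

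A patient is lost to observation only if the 30-day tail also ended in the gap, so

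*g* = 21 × [1 - exp(-h × (L - 30/365.25))], with L in years.

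| Assumed lag | *g*, h = 0.148 | *g*, h = 0.320 |
|---|---|---|
| 3 months | 0.5 | 1.1 |
| 6 months | 1.3 | 2.6 |
| 12 months | 2.7 | 5.3 |

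**4. Effect on a percentage, numerator held at 10.**

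| Denominator | Meaning | 10/n |
|---|---|---|
| 34 | Safety Set, as planned | 29.4% |
| 23 | *g* = 0 | 43.5% |
| 21 | *g* = 2 | 47.6% |
| 19 | *g* = 4 | 52.6% |

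Most of the shift, from 29.4% to 43.5%, comes from the 11 earlier leavers. Each patient leaving in the gap adds a further 2 to 3 percentage points. With 9 or 11 patients in the numerator, the figure on 23 is 39.1% or 47.8%.

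**5. Registry table (incidence above 5%).** On 34 an event needs two patients (1/34 = 2.9%, 2/34 = 5.9%). On 20 to 23 it still needs two (1/20 is exactly 5.0%). On 19 one patient is enough (1/19 = 5.3%).

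**6. Events never reported.** The one-sided 95% upper bound for zero events is 1 - 0.05^(1/n): 8.4% at n = 34, 12.2% at 23 and 14.6% at 19. The planned denominator makes the data look more reassuring than they are.

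**The case against.** **The date is only a filter.** The SAP calls it a general cutoff and does not claim that collection began everywhere that day. It also keeps incompletely captured earlier SAEs out of the RDC tables. That is fair, but the denominator does not change with the cutoff, and the bias lies in the denominator.

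**Collection in the gap may have been recovered.** A reader might infer that no non-serious event with onset in the gap could reach RDC. The documents do not support this. Protocol 8.1.1 defines adverse events from signed consent, and SAP 2.1 says about half of the pre-amendment SAEs were not in RDC, so about half were. Whether non-serious events were entered afterwards is not stated. For the same reason, moving the cutoff is not a remedy by itself: if nothing was collected in the gap, no non-serious numerator changes, and if events were entered later, a stricter cutoff would delete real ones.

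**The shortfall will be shown.** SAP 2.1 discloses incomplete collection, and SAP 2.8.1 plans a patient-level display. This is a real mitigation, but it alters no percentage, and the SAP does not define where each patient's collection period starts.

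**Serious events are covered.** This stands. SAP 2.8.2 tabulates SAEs, and AESIs reported as SAEs, from ARGUS for the whole study.

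**The patient-safety exception might apply.** The stated purpose of the amendment is to change the primary endpoint and to add AE collection and a benefit attestation. The amendment section requires approval first in any case.

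**It is a small descriptive study with no hypothesis test.** True, and this limits the severity. But the percentages are the primary result.

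**Conclusion.** The point holds as a denominator problem in the RDC non-serious AE and AESI tables. Patients whose on-treatment period ended before collection took effect for them count as event-free, so the percentages are biased low. The documented part is the 11 patients gone by release, less any whose 30-day tail overlapped collection. On the assumption that about 30% means 10 patients, none of them among those removed from the denominator, it is the difference between 29% and about 43%. Patients who left in the gap would take this to 48% on 21 or 53% on 19.

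A reader might infer that patients are known to have left between release and local implementation, or that the gap was long. Neither is documented. The ranges for *g* rest on assumed lags and a constant discontinuation rate, and at 3 months they amount to about one patient or fewer. A reader might also infer that SAE frequency is understated overall. It is not, because ARGUS covers SAEs throughout and only the RDC SAE tables are touched.

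This should be fixed. It affects the primary endpoint and is cheap to correct, but it does not undermine the study.

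**What to change.** In SAP 2.8.2, define for each patient an AE-collection start: the later of the first roll-over dose and the date Amendment 1 took effect for that patient (site approval, or re-consent if later). Then:

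- For the RDC non-serious AE and AESI tables, including the registry table with the 5% threshold, use as denominator the patients with on-treatment time on or after that date. Count numerator patients from the same group, and show the full Safety Set percentage alongside.
- Start the SAP 2.8.1 collection-period table and plot at the same date.
- Report how many patients left between 18-Mar-2016 and their own start date.
- Do not delete RDC events with onset after 18-Mar-2016 but before the patient's start date. List and flag them.
- Keep ARGUS as the source for SAE frequency.

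The cost is SAP wording, one derived date for each of 34 patients, and smaller denominators with wider uncertainty. The sponsor would have to assemble the site approval or re-consent dates; the documents do not say where these are recorded.
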